1.2 OBJECTIVES

1.2.1 Primary objectives

The primary objective of this study is to assess the effect of teriflunomide in comparison to placebo on disease activity as measured by time to first clinical relapse after randomization in children and adolescents 10 to 17 years of age with relapsing forms of multiple sclerosis.

1.2.2 Secondary objectives

The secondary objectives of this study are as follows:

- To assess the effect of teriflunomide in comparison to placebo on disease activity/progression measured by brain MRI and on cognitive function
- To evaluate the safety and tolerability of teriflunomide in comparison to placebo
- To evaluate the pharmacokinetics (PK) of teriflunomide.

[figure not shown]
1.3 DETERMINATION OF SAMPLE SIZE

The sample size calculation is based on the primary efficacy endpoint, time to first confirmed clinical relapse after randomization. Assuming 60% of placebo patients will experience a relapse by 2 years, 165 children aged 10 to 17 years (110 teriflunomide and 55 placebo; with at least 22 and 11, pre-pubertal, respectively) are needed for 80% power to detect a hazard ratio (teriflunomide versus placebo) of 0.5 (2-sided alpha 0.05). The 2-year rate of relapse in the teriflunomide group would be 36.8% and the corresponding hazard rates, assuming the time-to-relapse is exponentially distributed with a constant hazard rate, would be 0.4581 for placebo and 0.2291 for teriflunomide. The sample size is adjusted assuming 20% of patients discontinue the study in 2 years due to reasons other than relapse. Calculations are performed using nQuery Advisor 7.

The assumption for the percentage of placebo patients with relapse at 2 years is based on the combined data from the completed Phase III monotherapy adult studies (EFC6049/TEMPO and EFC10531/TOWER), where 58.7% of placebo patients aged ≤ 30 (n=167) experienced at least 1 relapse in a 2-year treatment period. Of note, the corresponding percentage was 38.7% in the 163 patients aged ≤ 30 treated with teriflunomide 14 mg.

1.4 STUDY PLAN

The study design is briefly described in the following graphical presentation:

R: Randomization

Note: An optional additional extension period with teriflunomide is offered to young patients when they complete the study, to provide treatment until they are 18 years old and/or can switch to commercial product, whichever comes first.

Table 1 - Study schedule for the double-blind period

Variable	Visit
Brain MRI	Screening, Weeks 24, 48, 72 and Week 96/end of treatment (EOT) ^a visit, Week 36 if necessary
EDSS	Screening, randomization, Weeks 24, 48, 72, Week 96/EOT ^a visit, and unscheduled relapse visits
SDMT	Randomization, Weeks 24, 48, 72, and Week 96/EOT ^a visit,
Cognitive Battery Test	Randomization and EOT ^a visit
Clinical Laboratory	Screening, randomization, every 4 weeks up to 24 weeks and then every 6 weeks up to the Week 96/EOT ^a
Vital signs	Screening, randomization, Weeks 4, 8, 12, 24, and every 12 weeks up to Week 96/EOT ^a visit
ECG	randomization, Week 96/EOT ^a and after EOT ^a if abnormality
Immunoglobulins and TSH	Randomization, Weeks 24, 48, 72 and Week 96/EOT ^a visit
PK	Weeks 2, 3, 4, 8, 12, 24, 36 and Week 96/EOT ^a visit
Physical examinations	Screening, randomization, Weeks 12, 24, and every 12 weeks up to Week 96/EOT ^a visit
Tanner assessment	Randomization, at Week 24, 48, 72, and at Week 96/EOT ^a for all patients (until complete sexual maturity).

^a Patients who complete the double-blind treatment period or who prematurely discontinue, should complete EOT visit.

Table 2 - Study schedule for the open-label period

Variable	Visit
Brain MRI	Weeks 48, 96, 144 and Week 192/end of treatment (EOT) ⁰ visit
EDSS	Weeks 24, 48, 72, 96, 120, 144, 168, Week 192/EOT ⁰ visit, and unscheduled relapse visits
SDMT	Weeks 24, 48, 72, 96, 120, 144, 168, Week 192/EOT ⁰ visit
Cognitive Battery Test	Week 96 and Week 192/EOT ⁰ visit
Clinical Laboratory	Transition, Weeks 4, 12, and then every 12 weeks up to the Week 192/EOT ⁰
Vital signs ^b	Transition, Weeks 4, 8, 12, and then every 12 weeks up to the Week 192/EOT ⁰
ECG	Week 192/EOT ⁰ and after EOT ⁰ if abnormality on EOT or ECG could not be performed at EOT (in exceptional circumstances).
Immunoglobulins and TSH	Week 96 and Week 192/EOT ⁰ visit
PK	Weeks 2, 3, 4, 8, 12, 24, 36 and Week 192/EOT ⁰ visit
Physical examinations	Weeks 12, 24, and then every 24 weeks up to the Week 192/EOT ⁰
Tanner assessment	Every 24 weeks up to the Week 192/EOT ⁰ for all patients (until complete sexual maturity).

Note: For a regional or national emergency declared by a governmental agency, contingency measures are included in the protocol section 17.7. Remote visits and unscheduled visits may be planned for the collection of possible safety and/or efficacy data.

a Patients who complete the open-label treatment period or who prematurely discontinue, should complete EOT visit

b During remote visits, only weight should be collected.

1.5 MODIFICATIONS TO THE STATISTICAL SECTION OF THE PROTOCOL

This statistical analysis plan (SAP) is specified for efficacy and safety analyses with all data collected in the open-label period for the open label CSR.

This section summarizes major changes to the protocol statistical section with emphasis on changes after study start (after the first patient was enrolled).

The statistical section of the protocol for open label period was never changed in an amendment.

1.6 STATISTICAL MODIFICATIONS MADE IN THE STATISTICAL ANALYSIS PLAN

In this section summarize major changes in statistical analysis features made in approved SAP versions, with emphasis on changes after study start (after the first patient was enrolled).

Statistical analysis for open-label period was not addressed in previous version of SAP or in amended protocol. The statistical analysis plan history table below gives the timing, rationale, and key details for major changes to the statistical analysis features in the statistical analysis plan. Changes also incorporated in a protocol amendment are cross-referenced to [Table 3](#).

Table 3 - Statistical analysis plan statistical changes

SAP version number	Date approved	Rationale	Description of statistical changes
1	05-May-2019	Many of the patients will be studied during the period of age-expected brain volume increase, thus brain atrophy is not appropriate	Replace "brain atrophy" to "percentage change of brain volume".
1	05-May-2019	To explore long-term treatment effect in teriflunomide/teriflunomide and placebo/teriflunomide group	Add annualized relapse rate (ARR) and time to sustained disability progression as additional endpoint in section 2.1.3.3 and 2.4.4.3.
2		To fulfill requirement from health authorities	Added ethnicity in the demographic section
2		To investigate Covid-19 impact on study conduct and assessment of safety and efficacy of teriflunomide	1) Added Covid-19 related disposition summary 2) Added extent of exposure and compliance summary for Covid-19 impact. 3) Added Covid-19 related adverse event analysis. 3) Modified censoring rule for time-to-event endpoint and OL EOT analysis visit window for potential Covid-19 delay.
2		To correct typo	Added 1 day for each of the target day and analysis visit windows in section 2.5.3

2 STATISTICAL AND ANALYTICAL PROCEDURES

The data from the double-blind and the open label teriflunomide treatment periods will be the focus of the CSR of their respective period. The following statistical methods/considerations in this SAP relate to the analysis of the data from the open label period. The analysis of the data from the double-blind period was addressed in a separate SAP. The optional additional extension period will be reported separately.

2.1 ANALYSIS ENDPOINTS

2.1.1 Demographic and baseline characteristics

The baseline value is defined as the last available value before the first intake of IMP in the double-blind period, unless otherwise specified.

All baseline safety and efficacy parameters (apart from those listed below) are presented along with the on-treatment summary statistics in the efficacy and safety sections (see [Section 2.4.4](#) and [Section 2.4.5](#)).

Demographic characteristics

Demographic variables are gender (Male, Female), race (Caucasian/white, Black, Asian/Oriental, other), ethnicity (Hispanic or Latino, Not Hispanic or Latino), region (definition of the regions are provided in [Section 2.5.5](#)), age in years at study consent of the double-blind period (quantitative and qualitative variable: <13, and ≥ 13 years), pubertal status, Tanner staging.

Medical or surgical history

Medical (or surgical) history includes concurrent illnesses, detailed neurological history and detailed vaccination history.

This information will be coded using the version of Medical Dictionary for Regulatory Activities (MedDRA) currently in effect at Sanofi at the time of database lock.

Disease characteristics at baseline

Specific disease history includes the following:

- Time since first diagnosis of Multiple sclerosis (MS) relative to randomization (in years)
- Time since first symptoms of MS relative to randomization (in years)
- Time since most recent relapse onset relative to randomization (in months)
- MS type (relapsing remitting, progressive relapsing)
- Number of relapses experienced within past 1 year (quantitative variable and qualitative variable: 0, 1, 2 and ≥ 3)

- Number of relapses experienced within past 2 years (quantitative variable and qualitative variable: 0, 1, 2, 3 and ≥ 4)
- Number of relapses experienced overall (quantitative variable and qualitative variable: 0, 1, 2, 3 and ≥ 4)
- With previous MS medication in the last 2 years (Yes, No)
- Total number of any events since onset of MS (0, 1, 2-5 and >5) and the subtype (Non encephalopathic Central nervous system (CNS) clinical events, Acute Disseminated Encephalomyelitis (ADEM), other event).

Vital signs

Vital signs at baseline as well as extension baseline (defined as the last available value before the first intake of IMP in the open-label extension period) are weight in kilograms (quantitative variable and qualitative variable: ≤ 40 , >40), height in cm, Body Mass Index (BMI) in kg/m^2 .

Other

Alcohol habits within the last 12 months and smoking habits will also be summarized.

Any technical details related to computation, dates, and imputation for missing dates are described in [Section 2.5](#).

2.1.2 Prior or concomitant medications

All medications taken during the open-label period are to be reported in the case report form (CRF) pages.

All medications will be coded using the World Health Organization-Drug Dictionary (WHO-DD) using the version currently in effect at Sanofi at the time of database lock.

- Prior medications are those the patient used prior to first investigational medicinal product (IMP) intake in the double-blind period. Prior medications can be discontinued before first IMP administration or can be ongoing during treatment period.
- Concomitant medications are any treatments received by the patient concomitantly to the IMP, from the day of first IMP intake in the double-blind period to the day of last IMP intake in the open-label period
- Follow-up medications are those the patient took running from the day after the last IMP intake in the open-label period up to the end of the open-label period

Any technical details related to computation, dates, imputation for missing dates are described in [Section 2.5](#).

2.1.3 Efficacy endpoints

Evaluation schedule for efficacy variables is presented in [Table 1](#) and [Table 2](#).

Note that all efficacy evaluations up to closeout measurement will be included for analysis unless otherwise specified. Baseline for efficacy variable is defined as the last non-missing value on or before the date of randomization in the double-blind period. For patients who have no value on or before randomization date, the last non-missing value on (at pre-dosing) or before the date of first dose intake in the double-blind period will be used as baseline.

2.1.3.1 Primary efficacy endpoint(s)

The primary efficacy endpoint is the time to first clinical relapse after randomization up to end of double-blind treatment period, which is not directly applicable for the open-label treatment period since Relapse Adjudication Panel (RAP) of the double-blind period was not continued into the open-label period. Refer to the SAP for the double-blind period of the study.

However, time to first clinical relapse after randomization in double-blind period up to the end of the open-label treatment period will be performed on relapses with objective signs on the Examining Neurologist's examination (which is the basis for RAP confirming relapses) as a primary efficacy endpoint for analysis period from randomization to the end of the open-label period.

2.1.3.2 Secondary efficacy endpoint(s)

The secondary efficacy endpoints pertaining to the open-label period are the following:

- Time to first clinical relapse since enrollment into the open-label period up to the exit of the open-label treatment period
- Proportion of clinical relapse free patients at 24, 48, 72, 96, 120, 144, 168 and 192 weeks
- MRI endpoints at 48, 96, 144 and 192 weeks:
 - Number of new/newly enlarged T2 lesions
 - Number of Gd-enhancing T1 lesions
 - Change in volume of T2 lesions
 - Change in volume of T1 hypointense lesions
 - Number of new hypointense T1 lesions
 - Proportion of patients free of new or enlarged MRI T2 lesions
 - Percentage change of brain volume

The number of new/newly enlarged T2 lesions and the number of Gd-enhancing T1 lesions will be considered the key secondary imaging endpoints.

- Cognitive outcome measured by the SDMT and Cognitive Battery Tests
- Teriflunomide PK
- Exploratory endpoint: proportion of disease-free patients.

2.1.3.3 Additional efficacy endpoints

The following endpoints, which have not been planned in the protocol for the double-blind period, are added as relevant for efficacy analysis of the open-label period.

- Annualized relapse rate (ARR) since the enrollment into the open-label period up to the exit of the open-label treatment period.
- Time to sustained disability progression (using EDSS) since randomization in double-blind period up to the end of open-label treatment period.

2.1.4 Safety endpoints

The safety analysis will be based on the reported adverse events and other safety information, such as clinical laboratory data, vital signs, ECG, etc.

Observation period

The observation period of the open-label period will be divided into 3 epochs:

- The **treatment** epoch is defined as the time from the first administration of the IMP in the open-label period to the last administration of the IMP in the open-label period.
- The **accelerated elimination** epoch is defined as the time from 1 day after the open-label treatment epoch up to 4 weeks (28 days) after the last administration of the IMP in the open-label period or up to the first administration in optional additional extension period, whichever occurs first.

The treatment-emergent adverse event (TEAE) period will include both treatment and accelerated elimination epochs.

- The **posttreatment** epoch is defined as the period of time starting from the day after the end of the treatment-emergent adverse event period up to the end of the open-label period (defined as the first dose of optional additional extension IMP for patients enter optional additional extension period, or the last protocol-planned visit, EOT +4W, in the open-label period or the resolution/stabilization of a followed-up AE for patients do not enter).

The on-study observation period is defined as the combination of TEAE period and posttreatment epoch.

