#### **10.1.3.4 Assessments performed on the EOT or premature treatment discontinuation**

Patients who complete the treatment period or who prematurely discontinue should complete EOT procedures including both safety and efficacy assessments. This visit does not need to be performed when the patient switches to the open label period after a confirmed relapse or high MRI activity (as per protocol criteria). Prematurely discontinued patients are encouraged to participate in an early permanent treatment discontinuation (EPTD): they will be followed for safety until they complete 96 weeks from randomization. This includes discontinuation from the open label period, when it occurs within 96 weeks of randomization.

- EDSS.
- SDMT.

- Cognitive Battery Test.
- Brain MRI.
- Adverse event reporting.
- Vital signs.
- Physical examination.
- ECG 12-leads.
- Tanner staging.
- Clinical routine laboratories (including immunoglobulins and TSH).
- Concomitant medication.
- Accountability / compliance.
- Teriflunomide PK sampling.

Post drug elimination process (ie, prescribing Cholestyramine or Activated charcoal and scheduling for two follow up visits) should be initiated.

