### **10.3.2 Definitive treatment discontinuation with investigational medicinal product(s)**

All patients who prematurely and permanently discontinue study medication will be asked to continue until the planned end of the double-blind treatment period EPTD. After completion of the premature discontinuation visit (EOT) and the post drug elimination follow-up visits, the patients continue to have study visits approximately every 12 weeks for clinical follow-up including EDSS, relapse reporting, AE reporting and Concomitant Medications recording.

In a specific emergency, participants who are close to the end of treatment may be unable to continue their final treatment as scheduled. These patients would be considered to have permanently discontinued their treatment ([Section 17.7](#)).

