2.1.4.2 Deaths

The deaths observation periods are per the observation periods defined above.

- Death on-study: deaths occurring during the on-study observation period

- Death on-treatment: deaths occurring during the treatment-emergent adverse event period
- Death post-study: deaths occurring after the end of the study (ie, the end of open-label period)

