Week (W) ^a	W102	W108	W114	W120	W126	W132	W138	W144	W150	W156	W162	W168	W174	W180	W186	W192/ EOT ^{b, u}	EOT +2W	EOT +4W	Relapse visit
Visit number ^r	20	21	22	23	24	25	26	27	28	29	30	31	32	33	34	35	36 ^c	37 ^c	
Treatments																			
Concomitant medications	X	X	X	X	X	X	X	X	X	X	X	X	X	X	X	X	X	X	X
Dispense study drugs/IVRS call		X		X		X		X		X		X		X		X ^t			
Accountability/co compliance		X		X		X		X		X		X		X		X			
Teriflunomide PK sampling ^k																X	X ^l	X ^l	

EOT = end of treatment (EOT= First visit after last study drug intake), EDSS = expanded disability status scale, FS = functional score, BVMTR = brief visuospatial memory test-revised, SDMT=symbol digit modalities test, MRI = magnetic resonance imaging, PK = pharmacokinetic.

- a The open label period starts by the transition visit. It is recommended that there is no time gap between the 2 periods, or as short as possible and if possible less than 2 weeks. In case of start of the open label period at the end of the 96 weeks of the double-blind period, the transition visit will generally coincide with the EOT visit of the double-blind period. Recommended windows: The window for obtaining biological samples at any given visit will be ±7 days. All other treatment period assessments should be completed within ±7 days of the scheduled visit date relative to the transition visit. Post drug elimination follow-up visits should be ±7 days of scheduled visit relative to end of treatment.
- b End-of-treatment and premature discontinuation visit.
- c For patients discontinuing treatment, 2 post drug elimination follow up visits should be scheduled 2 weeks and 4 weeks after study medication discontinuation and initiation of the drug elimination procedure. When applicable patients who prematurely and permanently discontinue study medication will be asked to continue until the planned end of double-blind period (ie, 96 weeks after randomization).
- d Re-consent before starting open-label period and after confirmed MS relapse and when patients turn adults as per local regulations.
- e During the adverse event reporting process, specific questions about pulmonary symptoms and peripheral neuropathy symptoms will be asked. (Patients will be instructed to alert the treating physician of symptoms suggestive of immunodeficiency).

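### The open-label SAP closes its posttreatment and on-study periods at EOT+4W, but patients who stop open-label drug early are followed to Week 96, so new AEs and SAEs in that follow-up have no table in this SAP

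*SAP*

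**What the plan says.** **Where the SAP stops.** Section 2.1.4 runs the treatment-emergent period "up to 4 weeks (28 days) after the last administration of the IMP in the open-label period", or to the first optional-extension dose if that is earlier. The posttreatment epoch starts the next day and lasts to the end of the open-label period. For patients who do not go on to the optional extension, that end is "the last protocol-planned visit, EOT +4W, in the open-label period", or the point at which a followed-up AE resolves or stabilizes. No rule says which of these two ends applies. The section adds: "The on-study observation period is defined as the combination of TEAE period and posttreatment epoch".

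**What depends on it.** Section 2.1.4.1 counts a posttreatment AE only if it started, worsened or turned serious inside that period. Section 2.4.5.1 builds the posttreatment AE and SAE tables from this definition. Section 2.1.4.2 defines: "Death post-study: deaths occurring after the end of the study (ie, the end of open-label period").

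**Where the protocol stops.** Protocol 10.1.3.4 describes early permanent treatment discontinuation (EPTD) follow-up for safety to 96 weeks from randomization, and states: "This includes discontinuation from the open label period, when it occurs within 96 weeks of randomization". Section 10.3.2 says that after the elimination visits "the patients continue to have study visits approximately every 12 weeks for clinical follow-up including EDSS, relapse reporting, AE reporting". Section 10.3.2.2 sets the end at Week 96 or AE recovery or stabilization, taking the later of the two. The SAP repeats the Week 96 rule: Appendix C, footnote c, says that patients who permanently "discontinue study medication will be asked to continue until the planned end of double-blind period (ie, 96 weeks after randomization").

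**The concern.** For a patient who switched to open label before Week 96 and then stopped drug, EOT+4W is not the last planned visit. The SAP therefore conflicts with the protocol and with its own appendix.

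The treatment-emergent period already reaches 28 days after the last dose, so a posttreatment epoch ending at EOT+4W has almost no length. A new AE or SAE found at a later EPTD visit comes after both windows and belongs to no AE table in this SAP. A death at that stage is put in the post-study category although the patient is still in planned follow-up.

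At stake is the description of what happens after children stop open-label drug early. The group is small, but individual SAEs matter in a 165-patient pediatric trial.

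**Working it through.** **1. Timeline.** The plan states no figure for this gap. The one related figure is the maximum open-label duration of 184 weeks (Appendix C, footnote r). It reproduces as 192 - 8 = 184, so the earliest open-label entry is Week 8.

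Take EOT at about the last dose. For a stop at week t after randomization, the on-study period ends at t + 4 and follow-up runs to Week 96:

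uncovered time = max(0, 96 - (t + 4)) = max(0, 92 - t) weeks.

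| Stop at week t | 8 (limit) | 12 | 24 | 48 | 72 | 84 | 92 or later |
|---|---|---|---|---|---|---|---|
| Uncovered weeks | 84 | 80 | 68 | 44 | 20 | 8 | 0 |

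**2. Length of the posttreatment epoch.** Treatment-emergent end: last dose + 28 days. EOT+4W: EOT + 28 days. With EOT at the last dose the difference is 28 - 28 = 0 days. It is up to 7 days with the visit window, and 14 days if the EOT visit is also 7 days late. It is longer only if an AE is still being followed.

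**3. Approximate number affected.** The documents do not give it, so this is a projection from the planning assumptions.

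- Hazards per year (SAP 1.3): 0.4581 for placebo (n = 55) and 0.2291 for teriflunomide (n = 110). Check against the plan: 1 - exp(-2 x 0.4581) = 0.600 and 1 - exp(-2 x 0.2291) = 0.368, which match its 60% and 36.8%.
- Weekly hazards, with a 52-week year: 0.4581/52 = 0.00881 and 0.2291/52 = 0.00441.
- Switch: only for a first relapse after the PK run-in (Protocol 5.1), so the switch week u runs from 8 to 96.
- Discontinuation (assumption): 20% at two years in both periods. The plan uses 20% for study discontinuation; applying it to open-label drug is my extension. The weekly hazard is h = -ln(0.8)/104 = 0.00215, or -ln(0.8)/96 = 0.00232 if two years means the 96-week period.

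For each arm, with relapse hazard L and r = 92 - u (set to 0 where negative), integrate over u:

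- switchers: n L exp(-(L + h)u)
- stops that lose time (before Week 92): the same density times 1 - exp(-hr)
- uncovered weeks: the same density times r - (1 - exp(-hr))/h

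Stops before Week 96 use 96 - u in place of r. Results, summed over arms:

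| Two-year discontinuation, spread over | Switchers | Stops before Week 92 | Stops before Week 96 | Uncovered patient-weeks |
|---|---|---|---|---|
| 10%, 104 weeks | 58.9 | 2.6 | 2.8 | 77 |
| 10%, 96 weeks | 58.6 | 2.8 | 3.0 | 83 |
| 20%, 104 weeks | 55.8 | 5.1 | 5.5 | 154 |
| 20%, 96 weeks | 55.4 | 5.5 | 5.9 | 165 |
| 30%, 104 weeks | 52.6 | 7.6 | 8.2 | 232 |
| 30%, 96 weeks | 51.9 | 8.1 | 8.7 | 247 |

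If the relapse hazards are also rescaled so that 96 weeks counts as the plan's two years, the 20% case gives 58.5 switchers, 5.8 stops before Week 92 and 177 patient-weeks.

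**4. After the fix.** With the period ending at the latest of EOT+4W, the last EPTD visit up to Week 96, and AE resolution or stabilization, the on-study period lasts as long as the follow-up and nothing is uncovered.

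**The case against.** **The double-blind report may cover these events.** Protocol 11.4.5 runs the double-blind post-treatment period from the end of the treatment-emergent period, which closes at open-label inclusion, to the end of the 96 weeks where applicable. Read literally, that could include this window. Section 5.1 also says the first study report includes data after treatment discontinuation as applicable. This objection stands as a limit: the double-blind SAP is a separate document and is not supplied. A reader might infer that the events vanish from all reporting, but the documents do not support that. The point is confined to the open-label SAP.

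**Other outputs exist.** Protocol 11.4.5 provides for separate summaries of non-treatment-emergent SAEs and for listings of all AEs, and SAP 1.1 says relevant double-blind methods carry over. Footnote c to SAP Table 7 ends the open-label period without an EOT+4W cap, although only for visit windows. These suggest loose drafting rather than a decision to exclude, but none of them puts the events into the posttreatment tables of SAP 2.4.5.1.

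**Deaths are not lost.** Correct. A reader might infer that they drop out of the report. SAP 2.4.5.2 tabulates on-study, on-treatment and post-study deaths and lists every death. The fault is the label.

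**A near-empty posttreatment epoch is often right.** Correct for stops at about Week 92 or later, where follow-up also ends at EOT+4W apart from unresolved AEs. The AE-resolution clause can lengthen the epoch, but it does nothing for a patient with no open AE at EOT+4W.

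**Follow-up is voluntary.** The protocol encourages or asks patients to continue, so the data exist only for those who agree. Data that are collected still need an analysis period.

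**Conclusion.** The point holds for the open-label SAP. Its end-of-period rule is wrong for patients who switch before Week 96 and stop open-label drug before about Week 92. Their later new AEs and SAEs fit neither AE definition in this SAP, and a later death is mislabelled post-study.

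It looks like an oversight. SAP 2.4.4.3.2 uses EDSS from follow-up visits after discontinuation to confirm 24-week progression, so the SAP uses post-stop follow-up for efficacy while its safety epochs leave it out.

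The size is small: about 5 to 6 patients and 150 to 165 patient-weeks at 20% discontinuation, and about 3 to 9 patients and 77 to 247 patient-weeks at 10% to 30%. This rests on the planning hazards, equal discontinuation in both periods, every eligible patient switching and every patient who stops accepting follow-up. Switches for high MRI activity would add to it. The 84 weeks is a limiting case: entry at Week 8 and an immediate stop.

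A reader might go further and conclude that the trial's safety conclusions rest on a truncated record. The documents do not support that: treatment-emergent events are the stated focus (SAP 2.4.5.1) and are unaffected, and coverage in the double-blind report is unknown.

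**What to change.** In SAP 2.1.4, for patients who do not enter the optional extension, define the end of the open-label period as the latest of:

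- the EOT+4W visit;
- the last EPTD follow-up visit, up to 96 weeks after randomization;
- resolution or stabilization of a followed-up AE.

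Carry this into the definitions of posttreatment AE (2.1.4.1) and of on-study and post-study death (2.1.4.2). The treatment-emergent period does not change. Add a line saying how events in this window are assigned between the double-blind and open-label reports, so that none is counted twice or missed.

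The cost is about one sentence plus the conforming definitions. The protocol already collects the data. The downside is a few more events in the posttreatment tables and the need to settle the overlap with the double-blind report.
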